6.3. INTRA-OPERATIVE CHARACTERISTICS

Evaluation Variable / Question	Level of Measurement	Analysis Plan	Inclusion		
Operative Visit – Operative Pro	cedure		IR	FR	N/A
Date of Surgery: (Variable(s): VISITDT; VISNAME)	Date/Time	Listing the first and last surgery in the report text to describe from which date to which date subjects were operated.		х	
Date of Admission: (Variable(s): ADMINDT; VISNAME)	Date/Time	None			Х
Date of Discharge: (Variable(s): DISCHRDT; VISNAME)	Date/Time	None			Х
Creation of variable Difference between Date of Admission [dd.mm.yyyy] and Date of Surgery [dd.mm.yyyy] in [days]] (Variable(s): ADMINDT; VISITDT; VISNAME)	Quantitative, ratio	Case summary with number and percentage of valid cases/values, missing cases/values (if any) and total cases/values. Mean, median, interquartile range, maximum, minimum, standard deviation, 95% confidence interval for mean, Shapiro-Wilk Test.		х	
Surgery Start Time (24 hour clock): (Variable(s): SURGSTTM)	Date/Time	None			Х
Surgery Stop Time (24 hour clock): (Variable(s): SURGSPTM)	Date/Time	None			Х
Difference between Surgery Start Time and Surgery Stop Time in / hh:mm / (Variable(s): SURGSTTM; SURGSPTM)	Quantitative, ratio Date/Time	Case summary with number and percentage of valid cases/values, missing cases/values (if any) and total cases/values. Mean, median, interquartile range, maximum, minimum, standard deviation, 95% confidence interval for mean, Shapiro-Wilk Test.		х	
Amount of Blood Infused (Variable(s): BLOODINF)	Quantitative, ratio	Case summary with number and percentage of valid cases/values, missing		Х	

		cases/values (if any) and total cases/values. Mean, median, interquartile range, maximum, minimum, standard deviation, 95% confidence interval for mean, Shapiro-Wilk Test.			
Type of Anesthesia: (Variable(s): TYPANEST)	Qualitative, nominal	Proportions, frequencies, column and row totals, missing proportion (if any).		X	
Were there any technical difficulties during surgery? (Variable(s): SURGDIFF; SURGDESC)	Qualitative, nominal	Proportions, frequencies, column and row totals, missing proportion (if any). Listing of given description.	x	x	
Were any concomitant procedure done during surgery? (Variable(s): CONPROC; CONPROCD)	Qualitative, nominal	Proportions, frequencies, column and row totals, missing proportion (if any). Listing of given description.	X	х	

Table 6.3.1: Operative Visit – Surgical Procedure Tables Li

Evaluation	Level of	Analysis Plan	Inclusion		n
Variable / Question	Measurement	7 1111 1 1 1 1 1 1 1 1			, II
Operative Visit – Implant Speci	fication and Loc	king Information	IR	FR	N/A
Nail Reference Number (xxxx/xxxx):	Qualitative,	None, used to populate nail			v
(Variable(s): REFNUM)	nominal	details into database			Λ
Approach (Variable(s): APPRCH)	Qualitative, nominal	Proportions, frequencies, column and row totals, missing proportion (if any).		Х	
Proximal Locking Mode (Variable(s): PROXLOCMD)	Qualitative, nominal	Proportions, frequencies, column and row totals, missing proportion (if any).		Х	
If Static Proximal Locking Mode (Variable(s): PRXOBLSTLSCR; PRXOBLANGSC; DISOBLSTLSCR; DISOBLANGLSCR; OBLSTLSCR; MLSTLSCR; MLSTANGLSCR)	Qualitative, nominal	Proportions, frequencies, column and row totals, missing proportion (if any).		х	
Distal Locking Screws (Variable(s): PROMLSTLSCR; PROMLANGLSCR; DISMLSTNLSCR; DISMLANGLSCR; APSTNLSCR; APANGLSCR)	Qualitative, nominal	Proportions, frequencies, column and row totals, missing proportion (if any).		х	
Was the Distal Targeting Device used? (Variable(s): DISTTARGT)	Qualitative, nominal	Proportions, frequencies, column and row totals, missing proportion (if any).		Х	
Was an End Cap used? (Variable(s): ENDCAP)	Qualitative, nominal	Proportions, frequencies, column and row totals, missing proportion (if any).		X	
If yes, check which length of End Cap was used (Variable(s): ENDCAPLENTH)	Qualitative, nominal	Proportions, frequencies, column and row totals, missing proportion (if any).		Х	

Table 6.3.2: Operative Visit – Implant Specification and Locking Information

6.4. EARLY POST-OPERATIVE CHARACTERISTICS

N/A

6.5. POST-OPERATIVE CHARACTERISTICS

The analysis of the Postoperative data must be performed separately for each follow-up visit listed in table 4.4 in accordance to the following tables in this chapter. New Variables must be created individually for each follow-up visit.

Evaluation	Level of						
Variable / Ouestion	Measurement	Analysis Plan	I	nclusio	n		
Post-Operative Visit Form – Ph	ysical Exam		IR	FR	N/A		
Date of Visit:	Date/Time	None			Х		
Creation of variable Difference between Date of Surgery [dd.mm.yyyy] and Date of Visit [dd.mm.yyyy] In [days] (Variable(s): VISITID; VISNAME)	Case summary with number and percentage of valid cases/values, missing cases/values (if any) and total cases/values.Quantitative, ratioMean, median, interquartile range, maximum, minimum, standard deviation, 95% confidence interval for mean, Shapire Wilk Tast		Quantitative, ratio Quanti			х	
Is the subject weight bearing? (Variable(s): WEIGHTBEAR)	Qualitative, nominal	Proportions, frequencies, column and row totals, missing proportion (if any).	Х	Х			
Specify, Full or Partial (Variable(s): FULPART)	Qualitative, nominal	Proportions, frequencies, column and row totals, missing proportion (if any).	Х	Х			
Is the subject using an external support? (Variable(s): EXTRSUPP)	Qualitative, nominal	Proportions, frequencies, column and row totals, missing proportion (if any).	X	Х			
Has the bone consolidated (consider weight-bearing, pain and imaging)? (Variable(s): BONECONS; EXPLN)	Qualitative, nominal	Proportions, frequencies, column and row totals, missing proportion (if any). Listing of given explanations.	Х	Х			

Table 6.5.1: Post-Operative Visit Form – Physical Exam Tables List

Evaluation	Level of Massurament			clusion	
Post-Onerative Visit Form – SF	-36 Score		IR	FR	N/A
In general, would you say your health is (Variable(s): GH01 RESPONSE)	Qualitative, nominal	Proportions, frequencies, column and row totals, missing proportion (if any).			X
Compared to one year ago, how would you rate your health in general now? (Variable(s): HT RESPONSE)	Qualitative, nominalProportions, frequencies, column and row totals, missing proportion (if any).				х
Vigorous activities, such as running, lifting heavy objects, participating in strenuous sports (Variable(s): PF01_RESPONSE)	Qualitative, nominalProportions, frequencies, column and row totals, missing proportion (if any).				Х
Moderate activities, such as moving a table, pushing a vacuum cleaner, bowling, or playing golf (Variable(s): PF02 RESPONSE)	Qualitative, nominal Proportions, frequencies, column and row totals, missing proportion (if any).				х
Lifting or carrying groceries (Variable(s): PF03_RESPONSE)	Qualitative, nominal	Qualitative, nominal Proportions, frequencies, column and row totals, missing proportion (if any).			Х
Climbing several flights of stairs (Variable(s): PF04_RESPONSE)	Qualitative, nominal	Qualitative, nominal Proportions, frequencies, column and row totals, missing proportion (if any).			Х
Climbing one flight of stairs (Variable(s): PF05_RESPONSE)	Qualitative, nominal	Proportions, frequencies, column and row totals, missing proportion (if any).			Х
Bending, kneeling, or stooping (Variable(s): PF06_RESPONSE)	Qualitative, nominal	Proportions, frequencies, column and row totals, missing proportion (if any).			Х
Walking more than a mile (Variable(s): PF07_RESPONSE)	Qualitative, nominal	Proportions, frequencies, column and row totals, missing proportion (if any).			Х
Walking several hundred yards (Variable(s): PF08_RESPONSE)	Qualitative, nominal	Proportions, frequencies, column and row totals, missing proportion (if any).			х

Walking one hundred yards (Variable(s): PF09_RESPONSE)	Qualitative, nominal	Proportions, frequencies, column and row totals, missing proportion (if any)		Х
Bathing or dressing yourself (Variable(s): PF10 RESPONSE)	Qualitative, nominal	Proportions, frequencies, column and row totals,		X
Cut down the amount of time you spent on work or other activities	Qualitative, nominal	Proportions, frequencies, column and row totals,		X
Accomplished less than you would like	Qualitative, nominal	Proportions, frequencies, column and row totals,		X
(Variable(s): KP02_KESPONSE) Were limited in the kind of work or other activities (Variable(s): RP02_RESPONSE)	Qualitative, nominal	Qualitative, nominal Proportions, frequencies, column and row totals,		X
Had difficulty performing the work or other activities (for example, it took	Qualitative,	Qualitative, Proportions, frequencies, column and row totals		X
extra effort) (Variable(s): RP04_RESPONSE)		missing proportion (if any).		
spent on work or other activities (Variable(s): RE01_RESPONSE)	Qualitative, nominal	column and row totals, missing proportion (if any).		Х
Accomplished less than you would like (Variable(s): RE02 RESPONSE)	Qualitative, nominal	Proportions, frequencies, column and row totals, missing proportion (if any).		Х
Did work or other activities less carefully than usual (Variable(s): RE03_RESPONSE)	Qualitative, nominal	Proportions, frequencies, column and row totals, missing proportion (if any).		X
During the past 4 weeks, to what extent has your physical health or emotional problems interfered with your normal social activities with family, friends, neighbors, or groups? (Variable(s): SF01_RESPONSE)	Qualitative, nominal	Proportions, frequencies, column and row totals, missing proportion (if any).		X
How much bodily pain have you had during the past 4 weeks? (Variable(s): BP01 RESPONSE)	Qualitative, nominal	Proportions, frequencies, column and row totals, missing proportion (if any).		X
During the past 4 weeks, how much did pain interfere with your normal work (including both work outside the home and housework)? (Variable(s): BP02 RESPONSE)	Qualitative, nominalProportions, frequencie column and row totals, missing proportion (if a			х
Did you feel full of life? (Variable(s): VT01_RESPONSE)	Qualitative, nominal	Proportions, frequencies, column and row totals, missing proportion (if any).		Х
Have you been very nervous? (Variable(s): MH01_RESPONSE)	Qualitative, nominal	Proportions, frequencies, column and row totals, missing proportion (if any).		Х
Have you felt so down in the dumps that nothing could cheer you up? (Variable(s): MH02_RESPONSE)	Qualitative, nominal	Proportions, frequencies, column and row totals, missing proportion (if any).		Х
Have you felt calm and peaceful? (Variable(s): MH03_RESPONSE)	Qualitative, nominal	Proportions, frequencies, column and row totals, missing proportion (if any).		X
Did you have a lot of energy? (Variable(s): VT02_RESPONSE)	Qualitative, nominal	Proportions, frequencies, column and row totals, missing proportion (if any).		Х
Have you felt downhearted and depressed? (Variable(s): MH04 RESPONSE)	Qualitative, nominal	Proportions, frequencies, column and row totals, missing proportion (if any).		X
Did you feel worn out? (Variable(s): VT03_RESPONSE)	Qualitative, nominal	Proportions, frequencies, column and row totals, missing proportion (if any).		X
Have you been happy? (Variable(s): MH05_RESPONSE)	Qualitative, nominal	Proportions, frequencies, column and row totals, missing proportion (if any).		Х

Did you feel tired? (Variable(s): VT04_RESPONSE)	Qualitative, nominal	Proportions, frequencies, column and row totals, missing proportion (if any)			X
During the past 4 weeks, how much		inissing proportion (if any).			
of the time has your physical health or emotional problems interfered with your social activities (like visiting friends, relatives, etc.)? (Variable(c): SE()2_RESPONSE)	Qualitative, nominal	Proportions, frequencies, column and row totals, missing proportion (if any).			Х
I seem to get sick a little easier than other people (Variable(s): GH02 RESPONSE)	Qualitative, nominal	Proportions, frequencies, column and row totals, missing proportion (if any).			X
I am as healthy as anybody I know (Variable(s): GH03_RESPONSE)	Qualitative, nominal	Proportions, frequencies, column and row totals, missing proportion (if any).			Х
I expect my health to get worse (Variable(s): GH04_RESPONSE)	Qualitative, nominal	Proportions, frequencies, column and row totals, missing proportion (if any).			Х
My health is excellent (Variable(s): GH05_RESPONSE)	Qualitative, nominal	Proportions, frequencies, column and row totals, missing proportion (if any).			Х
Physical Functioning (Variable(s): PFSCORE)	Quantitative, ratio	Case summary with number and percentage of valid cases/values, missing cases/values (if any) and total cases/values. Mean, median, interquartile range, maximum, minimum, standard deviation, 95% confidence interval for mean, Shapiro-Wilk Test.	x	X	
Role Physical (Variable(s): RPSCORE)	Quantitative, ratio	Case summary with number and percentage of valid cases/values, missing cases/values (if any) and total cases/values. Mean, median, interquartile range, maximum, minimum, standard deviation, 95% confidence interval for mean, Shapiro-Wilk Test.	x	x	
Bodily Pain (Variable(s): BPSCORE)	Quantitative, ratio	Case summary with number and percentage of valid cases/values, missing cases/values (if any) and total cases/values. Mean, median, interquartile range, maximum, minimum, standard deviation, 95% confidence interval for mean, Shapiro-Wilk Test.	X	X	
General Health (Variable(s): GHSCORE)	Quantitative, ratio	Case summary with number and percentage of valid cases/values, missing cases/values (if any) and total cases/values. Mean, median, interquartile range, maximum, minimum, standard deviation, 95% confidence interval for mean, Shapiro-Wilk Test.	X	X	
Vitality (Variable(s): VTSCORE)	Quantitative, ratio	Case summary with number and percentage of valid cases/values, missing cases/values (if any) and total cases/values. Mean, median, interquartile range, maximum, minimum,	X	X	

				1	
		standard deviation, 95% confidence interval for mean, Sharing Wills Tost			
Social Functioning (Variable(s): SFSCORE)	Quantitative, ratio	Case summary with number and percentage of valid cases/values, missing cases/values, missing cases/values (if any) and total cases/values. Mean, median, interquartile range, maximum, minimum, standard deviation, 95% confidence interval for mean, Shapiro-Wilk Test	x	x	
Role Emotional (Variable(s): RESCORE)	Quantitative, ratio	Case summary with number and percentage of valid cases/values, missing cases/values (if any) and total cases/values. Mean, median, interquartile range, maximum, minimum, standard deviation, 95% confidence interval for mean, Shapiro-Wilk Test.	x	x	
Mental Health (Variable(s): MHSCORE)	Quantitative, ratio	Case summary with number and percentage of valid cases/values, missing cases/values (if any) and total cases/values. Mean, median, interquartile range, maximum, minimum, standard deviation, 95% confidence interval for mean, Shapiro-Wilk Test.	x	x	
Total Physical Score (Variable(s): PCSSCORE)	Quantitative, ratio	Case summary with number and percentage of valid cases/values, missing cases/values (if any) and total cases/values. Mean, median, interquartile range, maximum, minimum, standard deviation, 95% confidence interval for mean, Shapiro-Wilk Test.	x	x	
Total Mental Score (Variable(s): MCSSCORE)	Quantitative, ratio	Case summary with number and percentage of valid cases/values, missing cases/values (if any) and total cases/values. Mean, median, interquartile range, maximum, minimum, standard deviation, 95% confidence interval for mean, Shapiro-Wilk Test.	х	х	

Table 6.5.2: Post-Operative Visit Form – SF-36 Score Tables List

6.6. ANALYSIS OF CI ENDPOINTS

Evaluation Variable / Question	Level of Measurement	Analysis Plan
Endpoints – Primary Endpoint		

Use variable SF-36 Total Physical Score 12 Months [points]:

Based on the underlying distribution of the data and the result of the normality assessment, either the parametric onesample t-test or the non-parametric one-sample sign test will be used to compare the 12 months post-operative SF-36 score results of the T2 Alpha Tibia group against the value of 39.25 points.

The complete available SPSS tables content related to either the one-sample t-test or the one-sample sign test will be included in the final report (under no circumstances, creation of this analysis in any interim/annual report). (Variable(s): VISITDT; PCSSCORE)

Evaluation Variable / Question	Level of Measurement	Recode and Analysis Plan	Ir	nclusio	n
All Assessments – Fracture Healing		IR	FR	N/A	
3 Months - 4. Has the bone consolidated (consider weight- bearing, pain and imaging)? (Variable(s): VISITDT; BONECONS)	Qualitative, nominal	Proportions, frequencies, column and row totals, missing proportion (if any).		X	
6 Months - 4. Has the bone consolidated (consider weight- bearing, pain and imaging)? (Variable(s): VISITDT; BONECONS)	Qualitative, nominal Proportions, frequencies, column and row totals, missing proportion (if any).			X	
12 Months - 4. Has the bone consolidated (consider weight- bearing, pain and imaging)? (Variable(s): VISITDT; BONECONS)	Qualitative, nominal	Proportions, frequencies, column and row totals, missing proportion (if any).		Х	

Table 6.6.1: Endpoints - Primary Endpoint Tables List

Table 6.6.2: Endpoints - Secondary Endpoint Fracture Healing Tables List

Evaluation Variable / Ouestion	Level of Measurement	Recode and Analysis Plan	Iı	nclusio	on
Adverse Events – Time to (earliest) Device Related Adverse Event / Incident			IR	FR	N/A
Creation of variable Difference between Date of Surgery [dd.mm.yyyy] and Date of First Device Related Adverse Event [dd.mm.yyyy] in [days] (Variable(s): VISITDT; VISNAME; AEONSTDT)	Quantitative, ratio	Case summary with number and percentage of valid cases/values, missing cases/values (if any) and total cases/values. Mean, median, interquartile range, maximum, minimum, standard deviation, 95% confidence interval for mean, Shapiro-Wilk Test.		х	
Creation of variable Difference between Date of Surgery [dd.mm.yyyy] and Date of 12 Months Visit [dd.mm.yyyy] in [days] (Variable(s): VISITDT; VISNAME)	Quantitative, ratio	N/A (Analyzed above), used for survivorship		Х	
Create new variable "Grouping variable – First Device Related Adverse Event" (Variable(s): AEEVENT)	Qualitative, nominal	- censored = survivors - events = first (earliest) Device Related Adverse Event		Х	
Create new variable "Combined Time – First Device Related Adverse Event" (Variable(s): AEONSTDT)	Quantitative, ratio	 Use time between surgery and 12 months visit for surviving subjects Use time between surgery and first device related adverse event for subjects with device related adverse event 		Х	
Use variables "Combined Time – First Device Related Adverse Event"	Qualitative,	Case summary with number and percentage of valid		Х	

and "Grouping variable – First Device Related Adverse Event"	nominal Quantitative, ratio	cases/values, missing cases/values (if any) and total cases/values. Kaplan-Meier survival analysis: subject ID, time, status, cumulative proportion, Kaplan-Meier estimate, standard error of KM estimate, number of cumulative events, number of remaining cases, mean for survival time with 95% confidence interval, survival graph bazard graph	
		survival graph, hazard graph.	

Table 6.6.3: Endpoints – Secondary Endpoint Time to (earliest) Device Related Adverse Event / Incident Tables List

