9.3. WITHDRAWAL CRITERIA

If, during the clinical investigation, a subject must be prematurely withdrawn, the procedures outlined in this section must be followed. These procedures should not interfere with the initiation of any new treatments that are necessary to treat a subject's condition. Information on all withdrawn subjects will be documented.

Subjects may be withdrawn from the clinical investigation for any of the following reasons:

- a. Subject Withdrawal: A subject may voluntarily withdraw from the clinical investigation at any time and for any reason. The subject should be asked when possible, and without any form of coercion, the reason for his/her decision. If the participant withdraws from the clinical investigation completely, then data collected up until the point of withdrawal will be included in the final analysis. Subjects who decline to continue to take part will be given the opportunity to discuss/inform the research team of the reasoning behind their decision not to take part.
- b. Lost to Follow-Up (LTFU): A subject will be considered LTFU after all reasonable efforts have been made to contact the subject and request his/her continued participation in the clinical investigation. All attempts to contact the subject must be documented and should include at least two attempts to contact the subject by phone and one attempt via a certified letter. Data collected up until the point where the subject is LTFU will be included in the final analysis.
- c. Removal of Device or Adverse Event/Incident: The discontinuation of a subject's participation in the clinical investigation due to the removal of the Tibial Nail of the T2 Alpha Tibia Nailing System or Adverse Event/incident that prohibits his/her continued participation must be fully explained. All available information concerning the removal of the device or Adverse

Event/incident should be provided. Data collected up until the point of removal or Adverse Event/incident will be included in the final analysis.

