3.1.1. Primary Analysis / Endpoint

This analysis is only part of the final report. The primary endpoint analysis will only be executed once at the end of the clinical investigation and will not be part of any interim or annual reports or presentations given in front of the final report.

The 12 months post-operative results for subjects implanted with the T2 Alpha Tibia Nailing System will be compared to Sanders et al: Semiextended intramedullary nailing of the tibia using a suprapatellar approach: radiographic results and clinical outcomes at a minimum of 12 months follow-up. J Orthop Trauma, 2014; Sun et al: The outcome comparison of the suprapatellar approach and infrapatellar approach for tibia intramedullary nailing. Int Orthop, 2016; and Chan et al: Suprapatellar Versus Infrapatellar Tibial Nail Insertion: A Prospective Randomized Control Pilot Study. J Orthop Trauma, 2016". Specifically, the SF-36 score results reported by Wang, et al. (2017), Sanders, et al. (2014), Sun, et al. (2016) and Chan, et al. (2016) will serve as the control groups for the T2 Alpha Tibia group.

Higher SF-36 PCS and MCS score results are linked to better subject results and vice versa.

The clinical investigation endpoint is non-inferiority to the control, meaning the clinical investigation result should be equal or better than the control. In this clinical investigation, an equal or better SF-36 score result means equal or greater (\geq). As only results from samples will be captured, results are mostly estimates of the true population parameter. These estimates vary by a certain area, where it is expected that the true population parameter falls within. Based on this, it is required to specify a lower limit for the acceptable difference or zone of indifference, denoted as - θ .

Hypotheses were developed to allow for a comparison of the 12 months post-operative SF-36 PCS to evaluate effectiveness / performance. The 12 months post-operative SF-36 PCS is the primary endpoint of this clinical investigation. Hypothesis tests will be one-sided with a significance level α of 5%.

Hypothesis	Equations	Interpretation	
Null (H ₀)	$A - B < -\theta$	Central tendency of A is inferior to	
	12 Alpha 11bia (A) – Control (B, pooled benchmark results) < $-\theta$	the central tendency of B.	
Alternative	$A - B \ge -\theta$	Central tendency of A is non-inferi	
(H ₁)	T2 Alpha Tibia (A) - Control (B, pooled benchmark results) $\geq -\theta$	to the central tendency of B.	

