This computation assumes that the population from which the sample will be drawn has a mean of 43.48 with a standard deviation of 13.04. The observed value will be tested against a theoretical value (constant) of 39.25.

This effect was selected as the smallest effect that would be important to detect, in the sense that any smaller effect would not be of clinical or substantive significance.

A second goal of this clinical investigation is to estimate the mean in the population. On average, a clinical investigation of this design would enable us to report the mean with a precision (95.0% confidence level) of plus/minus 2.77 points.

The precision estimated here is the median precision. Precision will vary as a function of the observed standard deviation (as well as sample size), and in any single clinical investigation will be narrower or wider than this estimate.

- Eile View Option	ns Tools Scenarios	Help	- 2 .			_181
Group	Population Mean	Standard Deviation	N of Cases	Standard Error	95% Lo w er	95% Upper
T2 Alpha Tibia IP & S	P 43,48	13,04	61 🔆	1,67	40,71	46,25
Lower Cr bound or be		Ę.				
Alpha= 0,050, Tails= 1		l		F	² ower = 0,805	
Alpha= 0,050, Tails= 1	ver	! 	x	F	⁹ ower = 0,805	
Alpha= 0,050, Tails= 1 Summary - Pov For the given effe constant of 39,22 is 0,805.	ver ct size (population mean= 4 5), sample size (61), and al	43,48, tested ag pha (0,050, 1-tai	ainst a led), power	F	² ower = 0,805	
Alpha= 0,050, Tails= 1 Summary - Pov For the given effer constant of 39,21 is 0,805. This means that 8 effect, rejecting th The test is one-ta direction can be s	ver tot size (population mean= 4 5), sample size (61), and al 1% of studies would be exp ne null hypothesis that the p illed, which means that only statistically significant.	43,48, tested ag pha (0,050, 1-tai pected to yield a opulation mean i an effect in the r	ainst a led), power significant s 39,25, expected	ŗ	⁹ ower = 0,805	

Estimated drop-out rate is 20% which leads to the requirement of enrolling additional 13 subjects into the clinical investigation.

Sample Size	Overall number of subjects to be enrolled: 74 subjects (rounded up to 80 subjects)

Table 3.2: Sample Size Justification

4. Methods

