4.4. TIMING OF OUTCOME ASSESSMENT

Subjects in this clinical investigation will be evaluated at Operative/Discharge, and at 3 Months, 6 Months and 12 Months after the index procedure. The follow-up evaluations will include assessment of device-related adverse events/incidents, evaluation per SF-36 PCS and MCS scores as well as clinical assessment of bone consolidation. Investigators should consider weight-bearing, pain and imaging when assessing bone consolidation. See the section below for visit windows and a list of assessments to be performed at each visit, given by the CIP.

Assessment	Operative/ Discharge	3 Months ^{a, b} (+/-2 weeks)	6 Months ^{a, b} (+/-3 weeks)	12 Months ^b (+/-4 weeks)		
Informed Consent	Xc					
Demographics & Medical History	Х					
Inclusion/Exclusion	Х					
Primary Diagnosis	Х					
Surgical Procedure	Х					
Clinical Assessment of Bone Consolidation ^{d, e}		Х	Х	Х		
SF-36v2 (PCS & MCS)	X f	Х	X ^g	X ^g		
Subject Disposition ^h		Х	Х	Х		
Device-Related Adverse Events/Incidents & Reoperations will be collected throughout the course of the Clinical Investigation.						

- a. Follow-up visit schedule to reflect Institutions' Standard of Care practices
- b. If the subject missed a visit and outside of visit window, every effort should be made to collect data instead of noting visit as missed. Visit windows are calculated from the index event, and not from the previous visit.
- c. Informed consent must be obtained prior to enrollment in the study (i.e., prior to performance of any study-related activities).
- d. Once bone consolidation is observed, assessment no longer needs to be conducted at the additional follow-up visits.
- e. Investigators should consider weight-bearing, pain and imaging when assessing bone consolidation.
- f. SF-36v2 evaluation must be collected post-informed consent. This can be collected post-fracture and prior to surgery or immediately post-surgery.
- g. If bone consolidation is previously observed at the previous follow-up visit, evaluation is to be collected via phone.
- h. Subject Disposition assessment would occur at any time point for subject withdrawal prior to the completion of the clinical investigation.

 Table 4.4: Assessments and Clinical Investigation Elements

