4.6. MISSING DATA

The intent is to collect as complete a dataset as possible. Nevertheless, in some situations missing data cannot be avoided. The reports and tables therefore will show the number and percentage of missing cases for each analyzed variable in relation to the enrolled cases for each post-operative assessment.

Missing data will be reported for each variable or calculation (if any) and overall totals will be reported including the proportion of missing data (if any).

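### The primary test uses only subjects with an observed month-12 PCS, and no missing-data method guards against drop-out bias

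*SAP*

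**What the plan says.** The primary endpoint table in SAP 6.6 opens with "Use variable SF-36 Total Physical Score 12 Months [points"] and uses a one-sample t-test, or a sign test if normality fails, to "compare the 12 months post-operative SF-36 score results of the T2 Alpha Tibia group against the value of 39.25 points". SAP 3.1.1 and protocol 11.3.2 describe the same test, and SAP 3.1.1 adds "Hypothesis tests will be one-sided with a significance level α of 5"%.

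On missing values, SAP 4.6 says "Missing data will be reported for each variable or calculation (if any") and that proportions missing will be shown. Protocol 11.4 likewise promises counts and percentages. Neither gives an imputation, a model or a sensitivity analysis.

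SAP 3.2 states "Estimated drop-out rate is 20"% and inflates 61 evaluable subjects to 74, rounded up to 80. The same section, like protocol 11.1, labels the rate a worst case.

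SAP 4.4 schedules "evaluation per SF-36 PCS and MCS scores" at the 3-, 6- and 12-month visits. Protocol 9.3 says for each way of leaving the study that data already collected are kept; for loss to follow-up the wording is "Data collected up until the point where the subject is LTFU will be included in the final analysis".

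**The concern.** Followed as written, the plan gives a completers-only result. The ITT population in SAP 5.1 is all enrolled subjects, but a one-sample test on month-12 PCS still omits every ITT subject without that score.

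The comparator is a fixed number, so there is no concurrent arm in which attrition bias could partly cancel. Protocol 9.3 lists device removal, adverse events and death among the reasons for leaving, so missing scores may well be related to outcome. If subjects who recover poorly leave more often, the completer mean is too high and a device at the non-inferiority limit passes too often. Enrolling extra subjects protects power but does nothing about this bias.

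**Working it through.** **Inputs from the documents.** Null value 39.25; assumed mean 43.48 and SD 13.04 (SAP 3.2: "This computation assumes that the population from which the sample will be drawn has a mean of 43.48 with a standard deviation of 13.04"); difference 43.48 − 39.25 = 4.23; one-sided α 0.05; 61 evaluable; 80 enrolled; drop-out 20%.

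**1. The plan's own figure.** Power is the probability that a noncentral t variable with n − 1 df and noncentrality 4.23/(SD/√n) exceeds the 95th percentile of t.
- n = 61: SE = 13.04/√61 = 1.670; noncentrality 4.23/1.670 = 2.53; power 0.805. This agrees with SAP 3.2.

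**2. Evaluable subjects and power at 20% drop-out.**
- 0.20 × 80 = 16 lost, 64 evaluable.
- SE = 13.04/√64 = 1.63; noncentrality 4.23/1.63 = 2.60; power 0.822. The planned loss does not underpower the test.

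**3. Bias of the completer mean.** Let drop-outs' true month-12 mean be D points below completers'. D is assumed; the documents give no value.
- All-enrolled mean = 0.8 × C + 0.2 × (C − D) = C − 0.2D, where C is the completer mean. The completer mean is therefore too high by 0.2D.
- Set the all-enrolled mean at exactly 39.25 and keep SD 13.04 and n = 64. The error is the chance that the 5% test passes, from the noncentral t with 63 df and noncentrality 0.2D/1.63.

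| D (points) | Bias (0.2D) | Noncentrality | One-sided error |
|---|---|---|---|
| 0 | 0 | 0 | 5% |
| 2.5 | 0.5 | 0.31 | 9.0% |
| 5 | 1.0 | 0.61 | 15.0% |
| 10 | 2.0 | 1.23 | 33.3% |

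A negative D (drop-outs doing better) reverses the bias and takes the error below 5%.

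**4. What the earlier PCS could add.** Suppose all 16 drop-outs have an earlier score with correlation ρ to month 12 (assumed). The effective sample size is then 1/[(1 − ρ²)/64 + ρ²/80].
- ρ = 0.5: 1/(0.75/64 + 0.25/80) = 67.4.
- Over ρ = 0.3 to 0.8 it is about 65 to 73, and power (normal approximation) rises from 0.829 to between 0.835 and 0.872.

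The precision gain is small, so the reason to use these scores is bias.

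**5. How much bias a likelihood model removes.** This was simulated with assumed inputs: 80 subjects, SD 13.04, PCS rising 5 points per visit, inter-visit correlations 0.4–0.5 or 0.6–0.7, and drop-out depending on the last observed PCS with odds ratio 2.0 per SD lower (22% missing, slightly above the plan's rate).
- Completers only: bias +0.9 to +1.3 points; error about 12.5% to 20% across repeat runs.
- Likelihood estimate using months 3 and 6: bias close to zero; error about 5%. This is a best case, because every simulated subject has a month-3 score, drop-out depends only on observed PCS, and the error was calculated from the estimator's simulated SD.
- When losses also occur before month 3 (about 19–20% missing), the likelihood estimate keeps a bias of roughly +0.2 to +0.6 points and an error of about 7% to 10%.

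**The case against.** Several stronger readings are tempting, and the documents do not support them.

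- **That the 3- and 6-month PCS is thrown away.** It is unused only in the primary test. SAP Table 6.5.2 summarises it by visit, Table 6.7.1 compares visits in paired tests and Table 6.7.6 analyses changes, all for the final report.
- **That the primary analysis contradicts protocol 9.3.** That section refers to the final analysis, not the primary test. Protocol 11.5.2 and SAP 4.3 describe the final analysis as the full final report, which includes those tables. What is missing is a statement of how such data bear on the primary endpoint.
- **That 20% is the expected loss.** The plan calls it a worst case, and there are safeguards: out-of-window data are still sought, PCS is taken by phone once consolidation has been seen, and loss to follow-up requires two calls and a certified letter. With fewer losses the bias shrinks in proportion.
- **That the error could be 26% to 41%.** Simulated figures of that size need 26% missing and a strong assumed link (odds ratio 3.3 per SD). The first exceeds the plan's worst case and the second is not in the documents.
- **That the bias must favour the device.** The documents give no direction. Well-recovered patients may also stop attending.

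It is also fair to say that a likelihood model is one option among several, multiple imputation being another, and that it is no complete cure. None of this supplies the missing rule: the primary test remains completers-only with no sensitivity analysis.

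**Conclusion.** The point holds as a risk of bias that the plan leaves unaddressed, not as a contradiction or a loss of power. That the primary test is completers-only, with no missing-data method, follows directly from the documents. At the worst-case 20% drop-out, 16 of 80 subjects do not count towards it. The consequence rests on an assumed difference between drop-outs and completers: an error of about 9% for 2.5 points, 15% for 5 and 33% for 10, against a nominal 5%. It would be nil if drop-out is unrelated to recovery. The change should be made before data freeze, because the remedy uses scores already scheduled and is hard to defend if chosen after the results are seen.

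**What to change.** In SAP 3.1.1 and 6.6 and protocol 11.3.2:

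- Estimate the month-12 mean PCS with a repeated-measures likelihood model (SPSS MIXED; visit at 3, 6 and 12 months as fixed effect; unstructured within-subject covariance; small-sample degrees of freedom). Include every treated subject with at least one post-operative PCS, and compare the one-sided 95% lower bound with 39.25.
- Keep the planned t-test or sign test on observed month-12 values as a supportive analysis, and say how the non-parametric rule in SAP 4.10 applies to the model.
- State how subjects who die or have the device removed are counted. Without this, the model implicitly projects a month-12 score for them.
- Report how many subjects have no post-operative PCS and how many contribute only 3- or 6-month scores.
- Add a tipping-point analysis that lowers the assumed month-12 PCS of subjects without one until the conclusion changes.
- Say in protocol 9.3 and SAP 4.6 how data from withdrawn subjects enter the primary analysis.

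The cost is wording in both documents and some extra analysis in software already named, with no added subjects or visits. The model assumes that drop-out depends on observed PCS and cannot correct for losses before month 3, which is why the tipping-point analysis is needed. The estimate may also be slightly less favourable than the completer mean.
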